## Abbreviations and Definitions

- Adverse Event (AE)
  - Any untoward medical occurrence associated with or observed in the context of a study procedure. For this study and patient population, an AE will be considered any suicidal ideation. No other events will be considered AEs as this patient population is ill and it is expected that other untoward medical occurrences will occur.
- Clinical Trial Management System (CTMS)
  - For this study, a CTMS known as OnCore will be utilized to manage the study's administrative responsibilities and subject level documentation.
- Duke Regional Hospital (DRH)
  - Study site in which eligible patients will be enrolled.
- Duke University Hospital (DUH)
  - Study site in which eligible patients will be enrolled.
- Electronic Data Capture (EDC)
  - For this study, the EDC will be supported by Pattern Health in which relevant study data, such as screening, enrollment, and clinical variables will be documented. Additionally, the study team will utilize RedCap, which is a secure, Duke approved EDC platform, in which the study screening and enrollment logs will be maintained.
- Electronic Health Record (EHR)
  - Used interchangeably with EMR; the EHR is the patient-specific medical record located in the secure MaestroCare (aka: EPIC).
- Electronic Medical Record (EMR)
  - Used interchangeably with EHR; the EMR is the patient-specific medical record located in the secure MaestroCare (aka: EPIC).
- Electronic Patient Reported Outcomes (ePRO)
  - ePRO can be used to describe study source, such as the patient-completed questionnaires (e.g., HADS, PHQ-10, PTSS), or can refer to the system that houses patient-derived data. For this study, ePRO may refer to the patient-questionnaires for psychological distress OR it may refer to the system, which houses the patient-derived data, which is the mCST app known as "Blueprint."
- Hospital Anxiety and Depression Scale survey (HADS)
  - Anxiety and depression symptoms
- Intensive Care Unit (ICU)
  - Defined as any medical, surgical, trauma, neurological, cardiac, or cardio-thoracic unit in which a patient is receiving cardiac or respiratory support for survival means.
- Institutional Review Board (IRB)
  - Ethical and regulatory committee who provides approval and oversight of clinical trial at study site.
- Mobile Coping Skills Training app (mCST, also known as 'Blueprint')
  - A native app that uses this downloaded as a self-contained program and is subject to the device operating system. The mCST created for this study known as "Blueprint", was developed, and is maintained by Pattern Health ([name]).
- Patient Health Questionnaire-10 (PHQ-10)
  - Physical symptoms
- Post-Traumatic Stress Scale survey (PTSS)
  - PTSD symptoms

- **Protocol Deviation (PD)**
  - An inadvertent event or event this is out of the control of the study team and/or the subject that occurs outside of the study protocol design and/or procedures.
- **Protocol Violation**
  - An act of intentionality that is committed by the study team and/or the subject that occurs outside of the study protocol design and/or procedures.
- **Serious Adverse Event (SAE)**
  - Defined as an adverse event that is both serious and expected in nature; the event may have a reasonable possibility that it is related to a study. SAEs for this study are defined as a suicide attempt, a hospitalization, or death.
- **Suicide Ideation (SI)**
  - The idea of committing self-harm and/or the intent to act on the idea of committing self-harm.
- **Unanticipated Problem (UP)**
  - Any other event, not meeting the definition of PD, UP, AE or SAE that, in the opinion of the principal investigator, merits documentation as it occurred outside the expected design of the study and/or study procedures. These events, like PDs, UPs, AEs, or SAEs, may be reported to the IRB and/or the study sponsor, as applicable.

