#### Adverse events (AEs), serious adverse events, (SAEs) and unanticipated problems (UPs).

It is recognized that there is a slight risk that some participants may become distressed when completing self-report measures or participating in interviews. When necessary, participants who experience psychological distress *related to completing questionnaires* will be referred for appropriate psychiatric or psychological care. All participants will have access to the PI’s contact information 24 hours a day (shown in the consent form). If a telephone interview is required, a trained study team member who has been trained to be sensitive to the nature of these issues will conduct it.

It is anticipated, in this study, for AEs to be extremely rare as it is a behavioral study. However, it is possible that participants could become distressed in a hospital setting or post-discharge due to increased illness and/or limitations. As such, participants could exhibit signs of and/or experience suicidal ideations or be admitted for mental health symptoms. Therefore, for this study, only increased levels of distress related to completing the questionnaires or completing the coping skills practice and/or suicidal ideations will be considered AEs.

Like, AEs, it is not anticipated that SAEs will occur. However, for this study, an SAE would be defined as a suicide attempt, a hospitalization (post hospitalization that initiated the patient’s eligibility for study

participation), or death. All serious adverse events will be reported within the standard timelines required to the IRB, study sponsor, and/or DSMB, as appropriate and when applicable.

Given the nature of this study, it is anticipated that most enrolled patients will not complete their study visits within the assigned protocol window. Additionally, it is expected that visits and/or mCST practices will be missed. As such, these will not be considered protocol deviations. Should other protocol deviations or unanticipated problems occur, they will be discussed with the PI, documented, and reported to the IRB, study sponsor, and/or DSMB, as appropriate and when applicable.

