#### Reporting Procedures

##### *Adverse and Serious Adverse Events*

For symptoms that are either great in total burden (i.e., total score is high), a delegated study team member (e.g., therapist) will call the participant to check in. For specific symptoms such as the suicidal ideation, a delegated study team member will also call the participant and assess the severity of the situation, triaging them as appropriate to psychiatric support.

For other matters, the study team will maintain frequent telephone contact with most participants, and can refer those with concerning symptoms.

All deaths will be reported to NHLBI Program Officer and to the DSMB Chair within 72 hours of study's knowledge of death. For each patient who dies, a brief report containing the following variables will be provided:

- Age
- Principal diagnosis
- Number of comorbidities
- Admission APACHE II score
- Days since enrollment
- Brief description of circumstances surrounding death including expected or unexpected.

Serious (fatal or life-threatening) SAEs that are unanticipated and that are related to the intervention will be reported to the NHLBI Program Officer and to the DSMB Chair within 7 days of study staff's knowledge of the SAE.

The summary of all other SAEs will be reported to NHLBI Program Officer and to the DSMB quarterly, unless otherwise requested by the DSMB.

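### The Protocol has two incompatible AE definitions, both worded as exhaustive, and one sentence requires an SAE to be expected, against its own event list and reporting rules

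*Protocol*

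**What the plan says.** **AEs.** The Protocol defines an AE twice.
- Abbreviations and Definitions: "For this study and patient population, an AE will be considered any suicidal ideation". It then closes the list: "No other events will be considered AEs as this patient population is ill".
- Section 12, under the heading on AEs, SAEs and UPs: "only increased levels of distress related to completing the questionnaires or completing the coping skills practice and/or suicidal ideations will be considered AEs".

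**SAEs.** The entry in Abbreviations and Definitions has two parts. The general part reads "Defined as an adverse event that is both serious and expected in nature". The study-specific part reads "SAEs for this study are defined as a suicide attempt, a hospitalization, or death". Section 12 gives the same three events: "an SAE would be defined as a suicide attempt, a hospitalization" (one after the qualifying admission) or death. It attaches no expectedness condition and says that "it is not anticipated that SAEs will occur".

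**Expectedness and reporting.** Under Expectedness in Section 12, the PI classes each event as expected or unexpected. Reporting Procedures has three tiers:
- all deaths go to the NHLBI Program Officer and the DSMB Chair within 72 hours;
- a 7-day report covers a narrower class: "Serious (fatal or life-threatening) SAEs that are unanticipated and that are related to the intervention will be reported";
- all other SAEs are summarised quarterly.

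**Oversight.** The DSMB part of Section 14 names AE reports and HADS scores as the primary safety measures. It also assigns the definitions of AEs, UPs and SAEs to the DSMB charter. The SAP plans no AE or SAE table.

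**The concern.** These are operative rules that tell staff what to enter and when to report, and two of them contradict other rules in the same document.

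For AEs, distress arising from the coping skills practice is a harm that the Protocol itself foresees: the Section 12 safeguards for severe distress say participants will be warned that the training may bring up distressing thoughts or feelings. Two staff members who each follow the Protocol faithfully could classify the same episode differently. Practice-related distress can arise only in the two app arms, because Arm 3 receives neither app nor therapist. The choice of page therefore bears directly on the AE counts of those arms and on their comparison with control.

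For SAEs, a definition that admits only expected events sits badly with a reporting rule written for unanticipated ones. At stake is whether a serious, unforeseen and intervention-related event reaches the DSMB Chair and the NHLBI Program Officer on the expedited timetable.

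**Working it through.** There is no figure to reproduce. The check sets the texts side by side and follows each reading through the reporting rules.

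**Step 1: the AE definitions.**

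| Event | Abbreviations and Definitions | Section 12 |
|---|---|---|
| Suicidal ideation | AE | AE |
| Increased distress related to the questionnaires | not an AE | AE |
| Increased distress related to the coping skills practice | not an AE | AE |

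The first text excludes everything except suicidal ideation. The second says that only its own items count. Neither leaves room for the other, so both cannot hold. Of Section 12's three categories, 3 − 1 = 2 drop out under the definitions list. This counts categories, not expected events.

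**Step 2: the SAE definition against its own premise.** The general sentence makes an SAE a kind of AE. Hospitalization and death are not AEs under the definitions list, so two of the three listed SAEs fail the definition that introduces them. Section 12's AE wording does not cover them either.

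**Step 3: the SAE definition against the reporting rule.** Take a suicide attempt that is life-threatening but not fatal, judged related to the intervention, and unexpected.

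| Reading | Is it an SAE? | Does the 7-day report apply? |
|---|---|---|
| Event list (either place), with the PI judging expectedness separately | yes | yes |
| General sentence taken literally, with unanticipated meaning not expected | no | no |

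Under the second reading no event can be both an SAE and unanticipated, so the 7-day class is empty.

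**Step 4: deaths.** The 72-hour rule covers every death, whatever its expectedness or relatedness, and is shorter than 7 days. Fatal events are therefore covered under every reading. What remains exposed is the non-fatal, life-threatening, related and unanticipated event, and only under the second reading.

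**Step 5: does another text settle it?** The SAP does not define AEs or SAEs. The charter might, but it is not among the documents, and the Protocol does not say that it overrides the Protocol's wording.

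**The case against.** A reader might infer two stronger conclusions, and the documents support neither.

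The first is that the 7-day report can never apply. The study-specific SAE sentence and Section 12 both list SAEs with no expectedness condition, and the PI is told to judge expectedness event by event. On those texts the rule works. It fails only if one general sentence overrides all of them and if unanticipated is equated with not expected. Deaths have their own faster rule.

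The second is that intervention-related distress goes unrecorded. Several routes do not depend on the AE label:
- concerns about severe distress, including distress without suicidality, go to the PI at once, and their resolution is entered in the contact log for the DSMB (Suicidality Response Plan);
- the DSMB reviews HADS scores and may ask for a formal test if they rise in a group;
- a distress score above the T1 value prompts contact at T2 and T3 (Study Visits);
- a high total symptom score prompts a call (Reporting Procedures);
- the PI may document other events as UPs.

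It is also fair to say that the charter may already reconcile the definitions, and that Section 12 expects AEs to be very rare.

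Most of this stands, and it narrows the point. It does not remove the contradiction. A rising HADS score or a contact-log entry need not show that the practice or the questionnaires caused the distress, and that attribution is what Section 12's AE definition turns on. UP documentation is at the PI's discretion. The DSMB part of Section 14 also calls for any adverse event to be reported immediately to the IRBs and the NHLBI Program Officer, so the AE label has consequences beyond the count.

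**Conclusion.** The point holds in a limited form and should be corrected.

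- **AEs:** the two definitions are incompatible as written. Questionnaire-related and practice-related distress, two of Section 12's three categories, count towards a primary DSMB safety measure under one text and not under the other. The exposure is in classification and counting; detection has other routes.
- **SAEs:** the general sentence conflicts with the study-specific sentence that follows it, with the Section 12 list, with the Expectedness rule and with Reporting Procedures. It also makes hospitalization and death a kind of AE, which the definitions list rules out. The expedited gap is confined to non-fatal, life-threatening, related, unanticipated events. It rests on two assumptions: that the general sentence is taken literally, and that unanticipated means not expected.

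The documents give no event rates for these categories, so the number of affected events cannot be stated. No sample size, benchmark or efficacy estimate depends on the point. It also assumes that the unseen charter has not already settled the definitions.

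**What to change.** 1. Reconcile the two AE texts into one definition and use it word for word in Abbreviations and Definitions and in Section 12. Check it against the DSMB charter definitions. The investigators and the DSMB choose the list.
2. Remove the expectedness condition from the SAE entry in Abbreviations and Definitions, so that expectedness is judged only under the Expectedness heading and the 7-day rule can operate.
3. In the same entry, resolve the statement that an SAE is a kind of AE, since the listed hospitalizations and deaths do not meet the AE definition.

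The cost is a short wording amendment and slightly more AE records. No arm, visit, sample size or analysis changes.

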## Clinical Protocol Synopsis

### 1. Title

Optimizing a self-directed mobile coping skills training intervention to improve cardiorespiratory failure survivors' psychological distress (aka: Blueprint).

### 2. Background

As survival has improved for the 2 million people with cardiorespiratory failure managed annually in the US, it has become apparent that these patients suffer from severe and persistent post-discharge symptoms of psychological distress including depression, anxiety, and post-traumatic stress disorder (PTSD). However, few targeted interventions exist that are relevant to patients' experiences and that accommodate their many physical, and social barriers to personalized care. To fill this gap, we have developed an innovative, native mobile coping skills training (CST) program that promotes automated care delivery and self-management of symptom-related distress. CST, by improving self-efficacy and adaptive coping, reduces psychological distress symptoms, thereby also improving quality of life.

Previous trials, in which this pilot randomized clinical trial (RCT) is based, have demonstrated that adaptive coping skills training (CST), is an active response for managing stressful events such as the experience of a critical illness. Cardiorespiratory failure survivors have emphasized in their own words the importance of coping to their perceived quality of life. While the use of adaptive coping skills (e.g., relaxation, positive reframing, problem solving) is associated with decreased psychological distress, survivors infrequently apply such strategies.

Therefore, we propose a 2-year project that will pilot CST via a native mobile app known as "Blueprint" in which 2 distinct aims will be operationalized and tested. Aim 1 focuses on usability prior to release for real patient use. For aim 1, 5 to 15 subjects will be recruited and enrolled and provide feedback on app use. Aim 2, which is the main focus of this project, is an RCT in which 60 eligible patients will be randomized to 1 of 3 arms in a 3:3:2 manner (i.e., n=25: n=25: n=10). The pilot RCT is both necessary and sufficient to inform a future definitive RCT designed to test a longer-term, self-directed mobile app version of CST. The pilot will ultimately aid in addressing key gaps identified in previous trials (CSTEP and LIFT RCTs). Both trials previously conducted raised questions about the ideal balance between the uses of a CST therapist versus the use of an app to deliver content. At the conclusion of this pilot study, we hope to have addressed the key questions raised in previous work and use the learned information to inform the conduct of a next-step multi-center RCT.

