### 3. Study Design

As mentioned in section 2, this project consists of two distinct aims: aim 1 (usability) and aim 2 (RCT). Aim 1 of this project will be conducted within a population of 5 to 15 healthy volunteers using a single study visit lasting approximately 30 to 60 minutes in which they will be asked to provide feedback on the app and its contents. Individuals enrolled into this aim will be asked to provide feedback via written communication. Feedback will be used to improve the app for Aim 2 (RCT).

Aim 2, which is the main focus of this exploratory pilot randomized clinical trial (RCT) is to be conducted within a population of 60 cardio-respiratory survivors with a 3-month follow-up. Eligible patients will be those individuals who are admitted to the hospital and receive treatment for cardio or respiratory failure. Additional characteristics of the target population are those that exhibit high psychological distress, as defined by their scoring at the time of hospital discharge via the Hospital Anxiety and Depression Scale (HADS) and Post Traumatic Stress Scale (PTSS) surveys. Eligible patients will be identified via daily electronic medical record (EMR) review and approached for consent while still hospitalized. Patients will be

asked to complete app registration and baseline survey completion post-consent, but at the time of hospitalization, if possible. Upon discharge, patients will be asked to complete survey 1, T1, to assess their levels of psychological distress. Should the patient demonstrate high enough levels of psychological distress, they will be randomized to 1 of 3 treatment arms:

- Arm 1: mCST Intervention Group 1 (self-directed coping skills training app with CST therapist intro call)
- Arm 2: mCST Intervention Group 2 (self-directed coping skills training app only)
- Arm 3: usual care (control group; no CST therapist and no coping skills training app)

Each participant, regardless of randomization arm will be asked to complete the following surveys at the listed time points below:

- Baseline (during hospitalization, post consent)
  - Collect sociodemographic data and establish baseline psychological distress.
- T1 (at the time of hospital discharge, within 1 week of returning to home but no more than 1 month (30 days) from discharge)
  - Complete the HADS, PTSS, and PHQ-10, QOL 100-point visual analog scale, IADL/ADLs
- T2 (1 month (30 days) post date of discharge; up to 2 months (60 days) for completion)

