## Study Visits

For aim 1, each participant will be asked to complete a singular study visit that last approximately 30-60 minutes. During this study visit, post consent, the individual will be asked to do the following:

- Find and install the Pattern Health app
- Register to the Blueprint study
- Complete baseline survey
- Randomize to 1 of 3 arms or screen fail purposely
- Provide feedback on app content and usability.

For aim 2, each consented patient will be asked to complete up to four individual study visits.

- **Baseline:** this visit is to occur post-consent (same day, ideally) at the time of hospital admission just prior to discharge. However, this visit may occur at the time of hospital discharge within 1-3 days of returning to home. At this visit, the following will occur:
  - App Registration
  - Baseline Survey Completion
- **T1 (Day 0) (+30 days):** this visit is to occur at the time of hospital discharge to home, ideally within the first week (7 days) of returning to home; however, it can occur up to 1 month (30 days) from the time of hospital discharge to home. At this visit, the patient will complete the T1 survey via the app, which includes the HADS, PTSS, and PHQ-10 surveys. Score dependent, the patient will be randomized to 1 of 3 arms: Group 1 (Blueprint app), Group 2 (Blueprint app + therapist), and Group 3 (control; no Blueprint app and no therapist). If the patient's psychological distress score is too low; he/she will receive an automated alert via the app describing they are not eligible and their study participation is complete.
- **T2 (Day 30) (+60 days):** this visit is to occur post 1 month randomization for those patients who remain eligible to participate in the study. HADS, PTSS, and PHQ-10 surveys will be administered again. If the patient's survey scores indicate high levels of distress, as defined by a triggered SI alert or increased distress score from T1, a delegated study team member will contact the patient for safety precautions.

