#### 8. Enrollment Sites

This study will be conducted at Duke University Health (DUH) and Duke Regional Hospital (DRH).

It is anticipated that between both sites, the study team will enroll approximately 2/3 of their population from DUH (~40 patients) and 1/3 from DRH (~20).

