### Sample Size and Power

This exploratory trial is not intended to test mCST's efficacy. While the 60-person sample size reflects the pragmatics of recruitment during a short enrollment period, it is large enough both to inform us about the potential challenges of delivering an app-based intervention in the context of post-discharge care as well as to provide meaningful confidence intervals for our estimates as was true for the similarly sized LIFT RCT (R34 AT00819).

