1.2 Study Hypotheses

1.2.1 Primary Hypothesis 1

The primary hypothesis is that the mobile CST app 'Blueprint' will be feasible and acceptable based on comparison of observed to a priori benchmarks.

1.2.2 Primary Hypothesis 2

The secondary hypothesis is, compared to usual care, the intervention participants will have improvement in symptoms of psychological distress (HADS and PTSS scores) at the 1 and 3 month timepoints (T2 and T3).

2 Study Design and Study Population

Participants are patients who were admitted to the ICU and were critically ill with either respiratory failure/insufficiency or cardiac failure/insufficiency. Additionally, participants experienced a high level of distress (HADS ≥ 8) at baseline.

This is a randomized clinical trial, where participants are consented and randomized to 1 of 3 arms (2 intervention arms, 1 control arm) in a 1:1:1 ratio. A total randomized sample size of 45 participants (15 per arm) was targeted. A method of minimization was used for randomization, with the aim to balance 3 stratification characteristics: ICU service (medical, surgical), baseline HADS score (<14 , ≥ 14), and age (<50 , ≥ 50).

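### Sample size, allocation ratio and arm labels do not agree: 3:3:2 of 60 is not 25:25:10, the SAP targets 45 at 1:1:1, and one protocol section swaps the therapist group

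*Protocol*

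**What the plan says.** **Size and ratio.** Protocol section 2 (Background) states, in one sentence, "60 eligible patients will be randomized to 1 of 3 arms in a 3:3:2 manner (i.e., n=25: n=25: n=10". The total of 60 recurs in section 3 ("to be conducted within a population of 60 cardio-respiratory survivors"), in section 8 ("the study team will enroll approximately 2/3 of their population from DUH (~40 patients) and 1/3 from DRH (~20") and in section 9, Sample Size and Power ("the 60-person sample size reflects the pragmatics of recruitment during a short enrollment period"). SAP section 2 (Study Design and Study Population) describes randomisation by minimisation "in a 1:1:1 ratio. A total randomized sample size of 45 participants (15 per arm) was targeted".

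**Arm identity.** Protocol section 3 defines "Arm 1: mCST Intervention Group 1 (self-directed coping skills training app with CST therapist intro call" and "Arm 2: mCST Intervention Group 2 (self-directed coping skills training app only". The SAP overview (section 1) and the SAP Appendix I tables use the same assignment. The T1 entry under Study Visits (section 7 in the protocol body, section 6 in its table of contents) gives "Group 1 (Blueprint app), Group 2 (Blueprint app + therapist), and Group 3 (control; no Blueprint app and no therapist", with the therapist in the other app group.

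**Coding.** SAP 3.2 derives trial arm from the platform variable Plan_name: the Group 1 label becomes Arm 1, Group 2 becomes Arm 2 and Control becomes Arm 3. It specifies no check against who actually received a therapist call.

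**The concern.** Total, ratio and arm counts fix the precision of the between-arm estimates and must match what the minimisation was programmed to do. Here one protocol sentence contradicts itself, and the SAP differs from the protocol on both total and ratio. Neither document as supplied explains the difference.

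The label conflict could change a result. Protocol section 2 says the earlier trials left open how to balance therapist and app, and section 9 plans exploratory comparisons of all three groups. The SAP model has a three-level arm factor, and the only between-arm rows in Table 4 are Arm 1 minus Arm 3 and Arm 2 minus Arm 3. If the platform's Group 1 and Group 2 followed the T1 visit text, those two rows would trade places, any Arm 1 versus Arm 2 difference would change sign, and by-arm results in the other tables would sit under the wrong heading. Nothing in the output would reveal it.

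**Working it through.** **1. The protocol's own figure.** Inputs from section 2: N = 60, ratio 3:3:2, stated counts 25, 25, 10. Formula: n_i = N × r_i / Σr.

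- 60 × 3/8 = 22.5 for each app arm, and 60 × 2/8 = 15 for control. The stated counts differ by 2.5, 2.5 and 5.
- Rounding does not rescue it. Whole-number splits of 60 near 3:3:2 are 22–23 : 22–23 : 15, and none gives a control arm of 10.
- Working back under 3:3:2, a control arm of 10 implies N = 10 × 8/2 = 40, and app arms of 25 imply N = 25 × 8/3 = 66.7.
- 25:25:10 divided by 5 is 5:5:2.

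**2. The SAP figure.** 45/3 = 15 per arm, which is internally correct but differs from the protocol in total and ratio.

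**3. Control share.** 10/60 = 17%; 15/60 = 25%; 15/45 = 33%.

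**4. Precision.** The documents give no SD, so results are in SD units of the analysed score for one time point, unadjusted, with everyone retained. Half-width of the 95% CI = t(0.975, N − 3) × √(1/n₁ + 1/n₂), with t = 2.0025 for N = 60 and 2.0181 for N = 45.

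| Comparison | 25:25:10 | 22.5:22.5:15 | 15:15:15 |
|---|---|---|---|
| Pooled app vs control | 50 vs 10: 0.69 | 45 vs 15: 0.60 | 30 vs 15: 0.64 |
| One app arm vs control | 25 vs 10: 0.75 | 22.5 vs 15: 0.67 | 15 vs 15: 0.74 |
| Arm 1 vs Arm 2 | 25 vs 25: 0.57 | 22.5 vs 22.5: 0.60 | 15 vs 15: 0.74 |

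First cell as an example: 2.0025 × √(1/50 + 1/10) = 2.0025 × 0.3464 = 0.694.

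**5. Retention benchmark of 80% (SAP 3.1).** Half-width = 1.96 × √(0.8 × 0.2 / n).

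- All randomised, as SAP Table 2 allows: 10.1 points (n = 60) or 11.7 points (n = 45).
- App recipients only, as protocol section 9 describes: 11.1 (n = 50), 11.7 (n = 45) or 14.3 points (n = 30).
- The eligibility, consent and randomisation benchmarks have denominators fixed before randomisation, so the arm split does not affect them.

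**6. Arm labels side by side.**

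| Source | Group 1 | Group 2 |
|---|---|---|
| Protocol section 3 | app + therapist call | app only |
| Protocol Study Visits, T1 | app only | app + therapist |
| SAP section 1 and Appendix I | app + therapist call | app only |
| SAP 3.2 | coded Arm 1 | coded Arm 2 |

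The coding is right only if the platform's labels follow protocol section 3. The documents do not describe the platform's configuration.

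**The case against.** - **Version drift.** The difference between 60 and 45 may come from different document versions. The SAP is dated 10/22/21 and speaks of the target and the minimisation in the past tense, while the protocol looks ahead and the supplied text carries no version date. The two also describe the care setting differently: any hospital setting in the protocol, and ICU, step-down or specialised units in the SAP. This stands as a possible explanation. It does not settle which came first, and it cannot explain the contradiction inside protocol section 2.
- **Label swap is conditional.** The formal arm definition and the whole SAP agree, and one list in a visit description is the outlier. Coding from a platform label is ordinary practice. All of this stands: a swap is a risk and not an established error. But the T1 visit is the step at which patients are assigned to a group, and the SAP has no independent check.
- **Little rides on the split.** The pilot disclaims efficacy testing and the SAP avoids p-values. For the contrasts in SAP Table 4, the protocol's stated counts and the SAP's counts are almost equally precise (0.75 and 0.74 SD). If the SD of the analysed score is close to the baseline SD, every between-arm half-width above exceeds the SAP's 0.5 SD yardstick under all three allocations. This stands, and it is why the case for correction does not rest on lost precision.
- **Illustrative half-widths.** The planned repeated-measures model depends on a within-patient correlation the documents do not give. This also stands.

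**Conclusion.** The inconsistencies are certain; their consequences are not. The protocol's ratio and counts for 60 patients cannot both be right, the SAP states a different total and ratio, and the protocol assigns the therapist call to both app groups in different places while the SAP relies on the group label.

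The effect on precision is modest. Across the three allocations, half-widths range from 0.60 to 0.69 SD for pooled app versus control, 0.67 to 0.75 SD for one app arm versus control, and 0.57 to 0.74 SD between the app arms, under the assumptions in the working. The size of any label effect cannot be computed from the documents. It would be nil for the protocol's pooled main comparison and a complete exchange of the two app arms in the SAP's by-arm results.

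This needs correction before analysis, because total, ratio and arm identity are basic facts of the trial and the analysis depends on a label that the protocol defines in two ways.

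**What to change.** 1. State one total, one ratio and matching counts, as actually programmed in the minimisation, in protocol section 2 and SAP section 2. Internally consistent options are 60 at 3:3:2 (22–23 : 22–23 : 15), 60 at 5:5:2 (25:25:10) or 45 at 1:1:1 (15:15:15). Protocol sections 3, 8 and 9 need editing only if 60 is not the final total.
2. If the target was changed, record the change and its date, in whichever direction it went.
3. Reconcile the T1 entry under Study Visits with protocol section 3 on which group has the therapist call.
4. Before analysis, verify the Plan_name mapping in SAP 3.2 against the platform's randomisation configuration and any record of therapist calls, and note the result in the SAP.

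The cost is a few wording changes, one change record if the target moved, and one configuration check. No further enrolment or data collection is needed.
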